Patients will be followed up at 1 week, 1 month, 3 months and 6 months after surgery. The distance and near angles of deviation, with and without glasses, and the angle disparity will be measured at each follow up visit and the ductions and versions were assessed in all patients.

Patients will be considered to have successful outcome if both the distance and near angles with spectacles were less than 8 PD esotropia/phoria. Patients who develop any exophoria/tropia, or in whom hyperopic correction needed to be reduced for treatment of a consecutive exotropia will be considered to be unsuccessful ^{6, 7, 15}. In addition, patients will be further subdivided into 2 groups according to the preoperative angle disparity into those with angle disparity 20 PD or less and those with angle disparity more than 20 PD. The success rate in each subgroup will be calculated.

For categorical variables (e.g., gender), percent distribution will be used. For continuous variables (e.g. age, angle of deviation), mean, range and standard deviation were used. Comparisons between the two groups will be done using t-test for independent samples for continuous variables

and chi square test for categorical variables. Statistical analysis will be performed with SPSS for Windows (SPSS Inc., Chicago, IL).

SAMPLE SIZE:

An estimation of sample size was performed considering a study power of 0.8 with an alpha error of 0.05 aiming to detect a difference of 5 Δ in the postoperative angle disparity between the 2 groups, assuming a postoperative standard deviation of 6 Δ⁹. Based on this estimation, a total of 24 eyes were found to be adequate in each group, and considering a 25% dropout during the follow-up, recruitment of 30 study subjects in each group will be targeted

EXPECTED START DATE: 1 January 2015

EXPECTED COMPLETION DATE: 31 December 2016

REFERENCES:

1. von Noorden G. Binocular vision and ocular motility (5th ed), St. Louis: Mosby. 1996: 307-308.
2. Parks M.. Concomitant esodeviations. In: Parks M.. Ocular Motility and Strabismus, Hagerstown: Harper & Row 1975: 99-111.

3. Prism Adaptation Study Research Group. (1990). Efficacy of prism adaptation in the surgical management of acquired esotropia. *Arch Ophthalmol* 1990; 108: 1248-55.

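### Success rates are planned on either side of a 20 PD disparity cut with no treatment-by-disparity estimate, so a chance difference between subgroups could be read as a rule for choosing the operation

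*Combined protocol and SAP*

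**What the plan says.** The METHODS paragraph that defines success also divides patients by preoperative angle disparity into "those with angle disparity 20 PD or less and those with angle disparity more than 20 PD". It then says: "The success rate in each subgroup will be calculated". It gives no reason for the cut, no expected share of patients on each side, and no expected success rate in either arm.

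The next METHODS paragraph gives the general rule for comparing the two treatment groups: a t-test for continuous variables "and chi square test for categorical variables". No interaction term, regression model, confidence interval or multiplicity rule appears anywhere.

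The SAMPLE SIZE section concerns a different, continuous outcome. The trial was sized "aiming to detect a difference of 5 Δ in the postoperative angle disparity between the 2 groups".

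**The concern.** Whether the treatment effect depends on disparity is a natural question in this trial, because disparity is built into the contrast between the arms. By METHODS, the augmented arm targets the average of the largest and smallest angles, and the Faden arm targets the smallest. The two targets therefore differ by (largest + smallest)/2 − smallest = (largest − smallest)/2, which is half the child's disparity. That gap grows continuously with disparity and has no step at 20 PD.

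The plan's only output on this question is a set of success rates in small subgroups. Rates alone do not show whether the effect differs between subgroups or how uncertain any difference is. A reader who sees a large gap between the arms on one side of 20 PD and a small gap on the other may conclude that the choice of operation should depend on disparity, when chance would produce that picture easily.

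**Working it through.** **Inputs from the document.** Power and alpha: "considering a study power of 0.8 with an alpha error of 0.05". Difference 5 PD; SD: "assuming a postoperative standard deviation of 6". Evaluable number: "a total of 24 eyes were found to be adequate in each group". Recruitment: "considering a 25% dropout during the follow-up, recruitment of 30 study subjects in each group will be targeted".

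**Assumptions, because the document is silent.** Two-sided tests; one observation per child; an even split at 20 PD, so m = 24/2 = 12 or 30/2 = 15 children per arm in each subgroup; and a range of success rates. A uniform effect means that the same pair of arm success rates holds in both subgroups.

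**Step 1: the plan's own figure.** n = 2(1.960 + 0.842)² × 6²/5² = 2 × 7.85 × 1.44 = 22.6, so 23 per group by the normal formula. The t-test solution is 23.6, so 24. The stated 24 is reproduced. That 0.8 power belongs to angle disparity and carries no information about power for success.

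**Step 2: rates only, no tests (the literal text).** Let D be the treatment difference in one subgroup minus that in the other. Under a uniform effect its mean is 0 and

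SE(D) = √{2[p₁(1−p₁) + p₂(1−p₂)]/m}.

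Example, 60% vs 80%, m = 12: √{2(0.24 + 0.16)/12} = √0.0667 = 25.8 points. The probabilities below are exact binomial.

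| Success by arm | SE, m = 12 | 20 points or more apart, m = 12 | SE, m = 15 | 20 points or more apart, m = 15 |
|---|---|---|---|---|
| 60% vs 60% | 28.3 | 46.2% | 25.3 | 51.0% |
| 60% vs 80% | 25.8 | 41.9% | 23.1 | 47.0% |
| 50% vs 80% | 26.1 | 42.5% | 23.4 | 47.6% |

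The 95% half-width for D runs from 1.96 × 23.1 = 45 to 1.96 × 28.3 = 55 points. (At m = 12 the differences move in steps of 1/12, so 20 points or more means 25 or more.)

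**Step 3: if chi-square were also applied within each subgroup (an inference).** With power p in each subgroup, the chance that exactly one is significant is 2p(1−p). Example, 50% vs 80%, m = 12: p = 0.357, giving 2 × 0.357 × 0.643 = 45.9%. By exact enumeration:

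| Success by arm | Chi-square, m = 12 | Chi-square, m = 15 | Fisher, m = 12 | Fisher, m = 15 |
|---|---|---|---|---|
| 50% vs 60% | 17.1% | 14.6% | 7.5% | 6.4% |
| 70% vs 80% | 14.3% | 18.3% | 6.1% | 7.7% |
| 50% vs 70% | 30.8% | 31.4% | 17.1% | 17.4% |
| 60% vs 80% | 30.0% | 35.7% | 16.7% | 19.8% |
| 70% vs 90% | 31.7% | 40.1% | 17.2% | 25.4% |
| 50% vs 80% | 45.9% | 48.7% | 33.2% | 37.1% |
| 60% vs 90% | 47.4% | 50.0% | 35.7% | 43.9% |

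The chi-square here is uncorrected. The range is about 14% to 50% by chi-square and 6% to 44% by Fisher's test. If 50% vs 80% is the only 30-point case, the upper ends are 49% and 37%. With no effect at all (60% in both arms, m = 12), at least one subgroup is significant in 1 − (1 − 0.059)² = 11.5% of trials by chi-square and about 4% by Fisher's test. One interaction test at the 0.05 level aims at a false signal of about 5%.

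**Step 4: what an interaction test can do.** With equal subgroups, the interaction has twice the standard error of the overall effect. An overall effect with 80% power sits at z = 2.80, so an interaction of the same size sits at 1.40. Its power is Φ(1.40 − 1.96) = Φ(−0.56), about 29%, and 80% power would need about four times the sample.

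**The case against.** The strongest reply is that the plan promises very little here. It says rates will be calculated. It names no test within subgroups, no significance rule and no claim that the effect varies. The chi-square rule is stated for comparing the two treatment groups, in a later paragraph. The subgroup is a single factor with one prespecified cut, and neither the sizing nor the main comparison depends on it. All of that stands.

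Two stronger readings are therefore unsupported. A reader might infer that success will be formally tested on each side of 20 PD; the text does not say so. A reader might also infer that a uniform effect will look confined to one subgroup nearly half the time. That figure needs a success difference of about 30 points, a roughly even split and uncorrected chi-square tests. The document gives no success rates and no split, and does not say which version of the test applies. For differences of 10 to 20 points the figure is about 14% to 40% by chi-square and 6% to 25% by Fisher's test.

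Nor do the documents allow the cost of cutting disparity at 20 PD to be put in numbers. A power gain from continuous disparity can be shown in an invented scenario, but only with a spread and slope that the plan does not give.

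It can also be said that an interaction test is too weak to be worth running. It is weak, as Step 4 shows. But that argues for an estimate with an interval, labelled exploratory; it does not make bare subgroup rates safer to interpret. A standard logistic interaction would be fragile. In a simulation with 24 per arm, assumed normally distributed disparity and uniform success of 70% vs 90%, about 10% of fits were separated or unstable. That limits the choice of model and leaves the need for an estimate in place.

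**Conclusion.** The concern holds in a limited form. The plan prespecifies success rates on either side of 20 PD and provides no estimate of whether the treatment effect changes with disparity. Step 2 carries the conclusion, because it needs no testing within subgroups: chance alone separates the two treatment differences by 20 points or more in about 42% to 51% of trials, given an even split, 12 to 15 children per cell and the success rates shown. Step 3 applies only if the general chi-square rule is carried into the subgroups, and its result depends heavily on success rates that the plan does not state.

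This is an inexpensive improvement to a secondary analysis. It does not undermine the main comparison between arms.

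**What to change.** Add the following to the analysis paragraph in METHODS:

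- Report success in each disparity subgroup by arm, with 95% confidence intervals, as description.
- Fit one exploratory treatment-by-preoperative-disparity interaction with disparity continuous. Lead with a linear model for 6-month angle disparity, the outcome on which the trial was sized.
- Support it with an interaction for success by a method that tolerates sparse cells, such as Firth logistic regression, or the difference between subgroup risk differences with its interval.
- State that any claim that the effect depends on disparity rests on the interaction estimate and its interval, and not on the result within one subgroup.

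The cost is a few sentences and one or two extra models. No new data are needed, because disparity is already measured before surgery and at each visit. The price is a weaker subgroup message: the interval will be wide and the power low, about 29% for an interaction as large as an overall effect with 80% power.

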All patients will receive a full ophthalmological assessment including history taking, measurement of uncorrected and best-corrected visual acuity, cycloplegic refraction, anterior segment examination, as well as a dilated fundus examination.

In addition, all patients will have a detailed motor examination during the initial evaluation and at each follow-up period. The angle of misalignment will be measured by the prism and alternating cover tests for both distance and near with and without glasses. The angle of horizontal misalignment will also be measured in side gazes and in straight up and down gazes. Measurement of the angle of deviation in up and down gazes will be done by tilting the head, approximately 25 degrees down and up respectively, with the patient fixing on a distance target. The difference between the angles of horizontal misalignment in up and down gazes will be used to calculate the amount of pattern strabismus if present.

The ductions and versions in all cardinal directions of gaze will be analyzed before surgery and thereafter during the postoperative follow up visits. Underaction will be measured on a 4-point

scale ranging from -1 to -4. Similarly overaction will be measured on a 4-point scale ranging from +1 to +4.

In all patients cycloplegic refraction will be performed using cyclopentolate 1% eye drops instilled 3 times 10 minutes apart with the last time 30 minutes before refraction. Patients with hypermetropia with a spherical equivalent $\geq +1.5$ D will then be prescribed the full cycloplegic refraction and then re-evaluated with spectacles one month later. Patients who appear to have a partially accommodative esotropia defined as residual esotropia >8 PD for distance with spectacles will have repeat refraction using atropine 1% drops 3 times a day for 3 days before refraction.

After ensuring that full cycloplegic refraction was prescribed, patients will then be evaluated with glasses to identify those with partially accommodative esotropia without convergence excess. Patients will be included in the study if the residual distance angle with cycloplegic prescription was > 15 PD. Patients with convergence excess esotropia, defined as the angle of deviation with glasses for near exceeding that for distance by 15 PD or more will be excluded from the study.

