Amblyopia will be defined as a difference of 0.3 logMAR in verbal children (3 lines on the standard logMAR visual acuity chart) or a strong unilateral fixation preference using an accommodative target in infants and preverbal children. All patients with amblyopia will be treated before surgery. In general amblyopia therapy was continued till there was no further improvement of visual acuity or fixation preference despite adequate compliance with therapy for an acceptable

duration. Amblyopia will be treated following the standard clinical practice using part-time occlusion and in concordance with the PEDIG guidelines ¹³. Anisometropia is defined as a difference in the spherical equivalent of both eyes by 1 D or more.

Patients with neurologic, ocular, or developmental disorders or follow-up less than 6 months will be excluded from the study. In addition, patients will be excluded if they showed oblique muscle dysfunction, vertical deviation, significant A or V patterns, paralytic or restrictive forms of strabismus, or had a history of prior eye muscle surgery.

The smallest angle of deviation is defined as the corrected angle for distance. The largest angle is defined as the angle for near measured without correction. The angle disparity is defined as the difference between the largest and smallest angles.

Patients will be randomly allocated using a random table to one of two groups. In one group bilateral augmented MR muscle recession will be performed (augmented group). In the other group bilateral MR muscle recession combined with posterior scleral fixation sutures will be performed (Faden group).

The surgeries will be performed by one of two surgeons ([name]) using the same surgical technique. In both groups the medial rectus muscle will be exposed and hooked through a limbal approach. The muscle will then secured with 6-0 polyglactin (Vicryl, Ethicon, Somerville, NJ) sutures.

In the augmented group, the medial rectus muscles will be recessed using standard tables ¹⁴ with the surgical dose targeting the average of the largest and smallest angles.

In the Faden group, medial rectus muscle recession will be performed as described above with the surgical dose targeting the smallest pre-operative angle. The muscle will then fixated to the sclera using 6/0 polyester sutures placed in a mattress like with the anterior and the posterior sutures passing through both the edge of muscle and the sclera 12 mm and 14 mm from the muscle insertion, respectively.

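### Postoperative angle disparity, the outcome the trial is sized on, is compared without adjusting for its preoperative value; adjustment is cheap, but the gain depends on a correlation the plan does not give

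*Combined protocol and SAP*

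**What the plan says.** The Sample Size section bases recruitment on one outcome, a difference of 5 PD "in the postoperative angle disparity between the 2 groups", with a postoperative SD of 6 PD, power 0.8 and alpha 0.05. The result is 24 per group.

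The statistical paragraph of Methods gives one test for every continuous outcome: "Comparisons between the two groups will be done using t-test for independent samples for continuous variables". It mentions no covariate, change score or other adjusted analysis. The follow-up paragraph schedules visits at 1 week and at 1, 3 and 6 months, "and the angle disparity will be measured at each follow up visit". It does not say which visit supplies the comparison on which the trial was sized.

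The baseline value exists. At the initial evaluation, "The angle of misalignment will be measured by the prism and alternating cover tests for both distance and near with and without glasses". Methods then defines the derived measure: "The angle disparity is defined as the difference between the largest and smallest angles". The largest is the uncorrected near angle and the smallest is the corrected distance angle. The only planned analytic use of the preoperative value is to divide patients "according to the preoperative angle disparity into those with angle disparity 20 PD or less and those with angle disparity more than 20 PD", for reporting success rates.

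**The concern.** When an outcome is also measured before treatment, a comparison of postoperative values alone leaves in the error term whatever variance the baseline explains. It also leaves in the estimate any chance difference between the groups at baseline. Here the outcome that drives the sample size has such a baseline. The 20 PD split does not do this job: it dichotomises the baseline and applies to success rates, not to mean disparity.

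The stake is precision only. The t-test holds its type I error, and its standard error already allows for chance imbalance. The questions are how much precision adjustment could recover with about 24 patients per group, and what it costs if the baseline turns out not to be predictive. A decision to adjust made after the baseline table has been seen is open to challenge, so the choice should be fixed beforehand.

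**Working it through.** **Inputs.** From Sample Size: difference 5 PD, SD 6 PD, alpha 0.05, power 0.8, n = 24 per group. Assumptions:
- The test is two-sided. The plan does not say, but a one-sided calculation gives 18 or 19, not 24.
- The 24 eyes per group are read as 24 patients, because disparity is one value per patient.
- The correlation r between preoperative and postoperative disparity is not in the documents, so a range is shown.

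**Reproducing the plan's figure.** The normal approximation gives n = 2 × (1.96 + 0.842)² × 6² / 5² = 22.6, so 23. The exact t-test gives 23.6, so 24. At 24 per group, with standardised difference 5/6 and 46 df, power is 0.807. The 95% CI half-width is t(0.975, 46) × 6 × √(2/24) = 2.013 × 1.732 = 3.49 PD. The plan's 24 is correct for the unadjusted t-test.

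**ANCOVA at the same n.** There are 45 df, and SE = 6 × √(1 − r²) × √[(2/24) × (1 + F/46)]. F follows F(1, 46) and represents chance imbalance in the covariate. Results are averaged over F.

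| Analysis | Power | 95% CI half-width (PD) |
|---|---|---|
| t-test | 0.807 | 3.49 |
| ANCOVA, r = 0 | 0.798 | 3.53 |
| ANCOVA, r = 0.1 | 0.802 | 3.51 |
| ANCOVA, r = 0.15 | 0.807 | 3.49 |
| ANCOVA, r = 0.2 | 0.814 | 3.46 |
| ANCOVA, r = 0.3 | 0.833 | 3.37 |
| ANCOVA, r = 0.5 | 0.897 | 3.05 |
| ANCOVA, r = 0.6 | 0.937 | 2.82 |

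The two analyses have equal power at r = 0.152.

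**Baseline predictive in the augmented arm only.** With equal SDs, the common slope is the mean of the two arm slopes, so the effective r is half the augmented-arm r.

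| Augmented-arm r | Effective r | Power | Half-width (PD) |
|---|---|---|---|
| 0.3 | 0.15 | 0.807 | 3.49 |
| 0.5 | 0.25 | 0.822 | 3.42 |
| 0.6 | 0.30 | 0.833 | 3.37 |

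Break-even in that arm is therefore about 0.30. Simulation of 200,000 trials per case gave power of 0.806, 0.822 and 0.835, with type I error of 0.0500, 0.0498 and 0.0503.

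**Chance baseline imbalance.** An imbalance of k standard errors shifts the unadjusted estimate by k × r × 6 × √(2/24) = 1.732 × k × r PD. The preoperative SD cancels.

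| r | Median imbalance, k = 0.674 (PD) | k = 1.96, reached in about 5% of randomisations (PD) |
|---|---|---|
| 0.2 | 0.23 | 0.68 |
| 0.3 | 0.35 | 1.02 |
| 0.5 | 0.58 | 1.70 |

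These shifts are random error already inside the t-test's interval, not bias.

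**The case against.** The strongest case against acting is that nothing is broken. The t-test is valid, the sample size was computed for it, and the benefit rests on a correlation that the documents do not supply. They even give reasons to expect a low one. The Introduction proposes posterior fixation because it may deal with the variability of the angle, which could leave little relation to baseline in that arm. In the augmented arm the operation depends on baseline disparity, "with the surgical dose targeting the average of the largest and smallest angles", which may weaken the relation there too. Methods also excludes patients whose near angle with glasses exceeds the distance angle by 15 PD or more, which may narrow the range of disparity. The larger gains, at r of 0.5 to 0.6 in both arms, have no support in the documents. All of this stands. It is why the point is optional and why the gain must be stated as conditional.

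Two further objections stand only in part. First, 6 months can be inferred as the analysis visit, because it is the last one and patients followed for less are excluded. It is still not stated for this comparison. Second, the two components of the covariate might come from different visits. The examination with and without glasses is placed at the initial evaluation, while afterwards the text says only: "After ensuring that full cycloplegic refraction was prescribed, patients will then be evaluated with glasses". Surgical planning and the 20 PD subgroups nevertheless require both angles before surgery, so the value will exist. Its definition needs a sentence.

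Finally, the figures assume 24 completers, whereas 30 recruits less 25% leaves 22.5. At 22 per group, power is 0.770 for the t-test, and 0.760, 0.798 and 0.868 for ANCOVA at r = 0, 0.3 and 0.5. That shortfall is a separate sample-size matter and does not change the comparison of the two analyses.

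**Conclusion.** The concern holds as a low-severity, optional improvement confined to postoperative angle disparity. Adjustment gains little at r of 0.2 or less (0.7 points of power at 0.2), about 2.6 points at 0.3 and 9.0 points at 0.5. Below about 0.15 it loses slightly, by at most 0.9 points of power and 0.04 PD of half-width at r = 0. If the baseline predicts outcome in the augmented arm only, the gain is about 2.6 points even at an augmented-arm r of 0.6.

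This rests on two-sided testing, one disparity value per patient, 24 completers per group, equal SDs and an assumed r. Confidence is medium because r is unknown. Adjustment would not repair any bias from excluding patients with less than 6 months of follow-up.

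**What to change.** In the statistical paragraph of Methods, the plan could:

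- Name the comparison on which the trial is sized as ANCOVA of angle disparity at 6 months, the last planned visit, with treatment as a factor and preoperative disparity as a continuous covariate.
- Define the covariate as the last measurement before surgery: near angle without correction minus distance angle in full cycloplegic correction. Say which visit supplies each component.
- Report the adjusted mean difference with its 95% CI, and keep the independent-samples t-test as a sensitivity analysis.
- Optionally, report the treatment-by-baseline interaction as an estimate with a CI, labelled supportive, because disparity enters the surgical target in one arm only. It will be imprecise at this size.

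No change is proposed for the other angles. The cost is wording only: no change in sample size and no new measurements, given that both components are already needed before surgery. SPSS, which the plan names, can fit the model. The statistical cost is one degree of freedom plus the allowance for chance imbalance, which together produce the worst-case loss given above. Naming the visit is worthwhile whatever the value of r.

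### The 25% dropout allowance is multiplied on rather than divided out: 30 per group keeps the required 24 only up to 20% dropout, and 24 eyes should read 24 patients

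*Combined protocol and SAP*

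**What the plan says.** The SAMPLE SIZE section bases the calculation on postoperative angle disparity, with a difference of 5 PD to be detected and an SD of 6 PD, "considering a study power of 0.8 with an alpha error of 0.05". It concludes that "a total of 24 eyes were found to be adequate in each group, and considering a 25% dropout during the follow-up, recruitment of 30" per group is the target, and it names the unit recruited in these words: "recruitment of 30 study subjects in each group will be targeted".

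Four statements in METHODS bear on this:

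- Analysis: "Comparisons between the two groups will be done using t-test for independent samples for continuous variables".
- Exclusions: patients with "follow-up less than 6 months will be excluded from the study".
- Allocation: "Patients will be randomly allocated using a random table to one of two groups". Surgery is bilateral in both groups.
- Outcome: "The angle disparity is defined as the difference between the largest and smallest angles". The largest angle is the uncorrected near angle and the smallest is the corrected distance angle.

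**The concern.** A dropout rate is a fraction of those recruited. If a fraction d is lost, the number to recruit is the required number divided by (1 - d). Multiplying by (1 + d) always gives too few. Here 30 matches the multiplication exactly, so the target does not deliver the 24 that the same sentence calls adequate.

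Dropouts also leave the analysis. The last scheduled visit is at 6 months, patients with shorter follow-up are excluded, and no method for keeping them in is described. At stake is whether the study has its stated power at its own assumed dropout.

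The unit is a second, smaller matter. The requirement is in eyes and the recruitment target is in subjects. A reader could take 24 eyes to mean 12 children with both eyes operated on.

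**Working it through.** **Inputs.** From SAMPLE SIZE: difference 5 PD, SD 6 PD, alpha 0.05, power 0.8, dropout 25%, equal groups. From METHODS: independent-samples t-test. The plan does not say whether alpha is one- or two-sided. I take it as two-sided, because a one-sided test needs 18.5, so 19, per group and does not reproduce 24.

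**Step 1: reproduce the 24.** The standardised difference is 5/6 = 0.833.

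- Normal approximation: n = 2 x (1.96 + 0.8416)² x (6/5)² = 22.6, so 23 per group.
- Noncentral t, matching the planned test: n = 23.6, so 24 per group. This is the plan's figure.

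**Step 2: reproduce the 30.**

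- 24 x 1.25 = 30, as stated.
- 24 / (1 - 0.25) = 24 / 0.75 = 32, the number that leaves 24 after a 25% loss.
- Starting from the normal-approximation 23 does not rescue the target: 23 / 0.75 = 30.7, so 31.

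**Step 3: what 30 per group leaves.**

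- At 25% dropout: 30 x 0.75 = 22.5 per group, or 45 of 60 in total, which splits 22/23.
- Dropout at which 24 remain: 1 - 24/30 = 20%.

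**Step 4: power for 5 PD with SD 6 PD, two-sided 0.05.**

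| Analysed per group | t-test | Normal approximation |
|---|---|---|
| 22/22 | 0.770 | 0.789 |
| 22/23 | 0.780 | 0.798 |
| 23/23 | 0.789 | 0.807 |
| 24/24 | 0.807 | 0.823 |
| 30/30 | 0.888 | 0.898 |

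The rows 22/22 and 23/23 are the two roundings of 22.5. They correspond to losses of 8/30 = 26.7% and 7/30 = 23.3%. Exactly 25% of 60 lost, split as evenly as possible, is the 22/23 row.

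The difference detectable with 0.8 power by the t-test is 5.19 PD at 22/22, 5.13 PD at 22/23 and 5.07 PD at 23/23.

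**Step 5: the unit.** Randomisation is by patient, and disparity is one near angle minus one distance angle, so each patient supplies one value. The 24 was used as a patient count, since 24 x 1.25 gives the 30 subjects. Read literally as 12 bilateral patients per group, it would give t-test power of only 0.50, which cannot be what was meant.

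**The case against.** The strongest objection is that the effect is too small to matter. The gap is 2 patients per group. At 25% loss the t-test shortfall is 2 points, and by the normal approximation power is 0.798, in practice the planned 0.8. A slightly wrong SD does as much: with 24 per group and an SD of 6.2 PD, t-test power is 0.781; with 22/23 and an SD of 5.8 PD it is 0.807. The SD is also borrowed from a study whose title names convergence excess and variable-angle infantile esotropia, while this trial excludes convergence excess. All of that stands as a statement about size. It does not make 30 follow from 24 and 25%.

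A second objection is that 25% may have been meant as a loose add-on, under which 30 is exact, and that the plan never expressly promises power 0.8 after a 25% loss. But the figure is called a dropout during follow-up, which is a rate of loss, and allowing for it has no purpose unless the required number remains.

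A third is that total loss matters more than the loss in either group: 23/25 retained still gives 0.806, and 22/26 gives 0.804. That is correct. Losing more than 6 of 30 in at least one group is necessary for power to fall below 0.8, but it is not sufficient.

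The last is that the eyes label is editorial, because the same sentence goes on to speak of subjects. I agree; it adds no weight to the arithmetic point.

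**Conclusion.** The concern holds. The base size of 24 per group is correct, but the recruitment target of 30 does not follow from it and the stated 25% dropout. Thirty per group covers 20%. At 25%, t-test power is about 0.78, with a range of 0.77 to 0.79 from rounding 22.5 per group: 1 to 3 points below the planned 0.8. With 20% dropout or less it is at least 0.807, and with none it is 0.888.

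This rests on a two-sided alpha, which is an assumption; on the plan's SD of 6 PD, whose source I could not check; and on dropouts being left out of the analysis, as the exclusion rule implies. The error affects a stated design figure and leaves the analysis itself unchanged. The unit label should be corrected but has no numerical consequence.

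**What to change.** Rewrite the closing sentence of SAMPLE SIZE along these lines: 24 patients per group are required, each giving one disparity value; recruiting 30 per group retains 24 at up to 20% dropout; at 25% dropout 22 or 23 per group remain, with power of about 0.78. State in the same place that alpha is two-sided, if that is so. This costs one sentence and no recruitment; the stated allowance or power becomes slightly less favourable.

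Only if 25% dropout and power 0.8 must both be kept would the target need to read 24 / 0.75 = 32 per group, 64 in total. That means 4 more patients. Given the size of the shortfall, the restatement is enough.
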